8.8.2 Inclusion criteria

All of the following inclusion criteria have to be fulfilled for enrollment of the patient to the clinical trial:

1. Standard indication for ICD or CRT-D therapy according to clinical practice
2. *De novo* implantation or upgrade/exchange^h (**group A** only) from existing ICD/CRT-Dⁱ or pacemaker implant
3. Patient is able to understand the nature of the clinical investigation and provides written informed consent
4. Patient is able and willing to complete all routine study visits at the investigational site
5. Patient accepts Home Monitoring concept
6. Age \geq 18 years

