8.8.3 Exclusion criteria

The following exclusion criteria shall **not** be fulfilled for enrollment of the patient:

1. Contraindication to ICD or CRT-D therapy, respectively
2. For CRT-D patients in **group A** only: physician not willing to activate MultiPole Pacing in the patient

^h Upgrade or exchange is not available for patients in group B due to possible interference between the previous implanted RV lead and the new implanted Plexa ICD lead (e.g. potential Adverse Events in which relation cannot be distinguished between both leads)

ⁱ Exchange of CRT-D device is only possible in group A, if patient is either already implanted with BIOTRONIK Sentus OTW QP lead or replacement of the LV lead is planned.

3. Cardiac surgical procedure planned within 6 months after implantation (including also interventional procedures like ablation, valve replacement etc.). Procedures to occur during or prior to implantation are not exclusionary.
4. Expected to receive heart transplant or ventricular assist device within 6 months
5. Life expectancy less than 6 months
6. Participation in any other interventional clinical investigation^j
7. Pregnant or breast feeding at time of enrollment

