9 STUDY PROCEDURES

9.1 Overview

Table 7 provides an overview of the study procedures.

Tab. 7: Time schedule and procedures for all patients. Group specific procedures of group A are displayed in blue, and group specific procedures of group B are displayed in green.

Investigations	Enroll-ment	Implan-tation	Pre-hospital discharge	Month 3 ± 30 days	Month 6 ± 30 days
Patient informed consent	x				
Verification of in- and exclusion criteria	x				
Demographic data	x				
Indication for ICD or CRT-D therapy	x				
ECG diagnostics (if available)	x				
NYHA class (if available)	x				X (CRT-D only)
Heart Failure Parameters (LVEF) (if available)	x				
Physicians evaluation responders/non-responders (CRT-D only)					x
Co-morbidities	x				
Cardiovascular medication	x				
Decision on group participation		x			
ICD/CRT-D system implantation		x			
Information / Measurements on DX devices (only if DX is implanted)		x	x	x	x
Device statistics CRT pacing, atrial burden (CRT-D only)			x	x	x
Programming/Handling/Change of programming of MPP		(x)	x	x	x
Programming of device settings		(x)	x		
Programming / Information on Early ATP one-shot		x			
Lead measurements with PSA		x			

Document the handling of Plexa ICD lead		x			
IEGMs of pacing and sensing test / Evaluation of appropriate sensing/pacing				x	
IEGMs / evaluation of ATP one shot success		x	x	x	x
IEGMs and documentation of ventricular tachycardia therapy episodes		x	x	x	x
IEGMs and documentation of the last 3 episodes with fast ventricular rhythm (e.g. SVTs, nVTs) prior to a follow-up		x	x	x	x
Lead measurements		x	x	x	x
IEGMs of all medical episodes (ventricular and atrial episodes, non-sustained VTs and fast intervals)		x	x	x	x
Documentation of MRI examinations, if applicable		x	x	x	x
Adverse event reporting	x	x	x	x	x
Device deficiency reporting		x	x	x	x
Regular study termination					x

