9.3 Implantation

All patients will be **either** implanted with one of the Ilivia ICDs (**group A**) **and/or** the Plexa ICD lead (**group B**). If both devices are implanted patients will participate in both groups as long as enrollment in both groups is still ongoing. Implantation shall be performed within 30 days after enrollment of the patient to the study.

Patients with planned pacemaker or ICD upgrade to ICD or CRT-D or exchange can also be included in the study (**group A** only).

The specific requirements of the implantation procedures are listed below:

1. Perform lead measurements prior to connection to the device. For patients in **group B** only measurements of the RV lead are required. Pacing thresholds for RA and RV lead have to be measured at a pulse width of 0.4ms. For CRT patients in **group A**, threshold measurements of at least the 6 recommended LV vectors is recommended to ensure availability of a suitable vector combination for MPP programming.
2. After lead connection to the ICD or CRT-D device, the following data have to be recorded during this follow-up:
 - Pacing thresholds measured manually or triggered automatically. In the RA and RV the pulse width must be 0.4 ms, in the LV any pulse width can be chosen. For patients in **group B** only measurement of the RV lead is required. For CRT-D patients in **group A** pacing thresholds in all 12 available LV vectors have to be measured, if MPP programming is already planned at this point in time.
 - P/R-wave sensing amplitude (mean value) of all channels (or RV lead only (**group B**)) including also atrial sensing amplitude in DX leads.
 - Pacing impedance of all channels (or RV lead only (**group B**)). For the LV channel, measurement of the pacing threshold automatically also provides impedance measurement values.
 - Painless shock impedance Pacing polarities of the LV channels (CRT-D only (**group A**))
3. **Group A:** Program and document settings for MPP and evaluate handling of the programming function of the programmer. For programming follow the recommendations provided in section 8.5.6. Document all information on the eCRF "MultiPole Pacing". MPP programming can be delayed but has to be finalized latest at Pre-hospital discharge.

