7.3. Plexa Analysis Set

Similar to the definition of the Ilivia analysis set (see chapter 7.2), the Plexa analysis set consists of all patients in group B and in group AB, who met all in- and exclusion criteria. Patients who did not come in contact with any Plexa lead are not included in the analysis set.

Data file, identifier patient_display_id_full	Variable name	Variable label	Variable level	Nominal values
enrollment	DMSUBIC	Patient has provided written informed consent	nominal	Yes /No
enrollment	TIINCL01 TIINCL02 TIINCL03 TIINCL04 TIINCL05 TIINCL06	Inclusion criteria [...]	nominal	Yes /No
enrollment	TIEXCL01 TIEXCL02 TIEXCL03 TIEXCL04 TIEXCL05 TIEXCL06 TIEXCL07	Exclusion criteria [...]	nominal	Yes /No
implantation_gene ral_data	imp_group	Patient Group		Device of the Ilivia family (group A) Plexa right ventricular lead (group B) Both Ilivia and Plexa (group AB)
study_termination	end_early_b	Reason for early study termination	nominal	Implantation of Plexa lead was planned but not performed (patient did not come in contact with the investigational device) [...]
study_termination	end_early_ab	Reason for early study termination	nominal	Implantation of Ilivia ICD family and Plexa lead were planned but not performed (patient did not come in contact with the investigational devices) [...]
data_SAR	analysis_set_Plexa_ SAR ⁶	Analysis set Plexa	nominal	Yes / No

⁶ IF DMSUBIC = Yes AND
 TIINCL01 = Yes AND TIINCL02 = Yes AND TIINCL03 = Yes AND
 TIINCL04 = Yes AND TIINCL05 = Yes AND TIINCL06 = Yes AND
 TIEXCL01 = No AND TIEXCL02 = No AND TIEXCL03 = No AND
 TIEXCL04 = No AND TIEXCL05 = No AND TIEXCL06 = No AND TIEXCL07 = No AND
 (imp_group = ... (group B) OR imp_group = ... (group AB)) AND
 end_early_b ≠ Implantation of Plexa lead was planned but not performed ... AND
 end_early_ab ≠ Implantation of Ilivia ICD family and Plexa lead were planned but not performed ...
 THEN analysis_set_Plexa_SAR = Yes
 ELSE analysis_set_Plexa_SAR = No

8. General data

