10.2. Variables

Implantation / ICD/CRTD

Data file, identifier patient_display_id_full	Descriptive	Variable name	Variable label	Variable level	Nominal values
implantation_general_data	Yes	imp_category	Study implantation	nominal	De novo CRT-D / ICD implantation Upgrade from pacemaker [...] Upgrade from ICD [...] Exchange of ICD / CRT-D [...]
implantation_general_data	Yes	imp_site	Implantation site	nominal	left / right
implantation_general_data	Yes	imp_dev_type_other	Device type	nominal	Single chamber ICD Dual Chamber ICD CRT-D
implantation_general_data	Yes	imp_dev	Device model	nominal	Ilivia 7 [...]
implantation_general_data	Yes	imp_dev_type	Device type	nominal	VR-T [...]
implantation_general_data	Yes	imp_connector	Connector type for RV lead	nominal	DF-1 / DF4

Implantation / Leads

Data file, identifier patient_display_id_full	Descriptive	Variable name	Variable label	Variable level	Nominal values
implantation_general_data	No	imp_rv_model	RV lead model	Nominal	Plexa S [...]
data_SAR	Yes	imp_rv_model_SAR ²⁴	RV lead model	Nominal	Plexa Other

²³ analysis_set_Ilivia_SAR = Yes

²⁴ IF imp_rv_model = Plexa S OR Plexa SD OR Plexa DF-1 S OR Plexa DF-1 SD or Plexa DF-1 S DX
THEN imp_rv_model_SAR = Plexa
ELSE imp_rv_model_SAR = other

Implantation Analyzer Data / RA

Data file, identifier_patient_display_id_full	Descriptive	Variable name	Variable label NEW prefix added to all labels "Implantation analyzer data, RA: "	Variable level	Nominal values
implantation_analyzer_data	Yes	imp_ana_ra_amp	Sensing amplitude [mV]	scale	n.a.
implantation_analyzer_data	Yes	imp_ana_ra_imp	Pacing impedance [Ω]	scale	n.a.
implantation_analyzer_data	Yes	imp_ana_ra_thresh	Pacing threshold [V] at Pulse width 0.4 ms	scale	n.a.
implantation_analyzer_data	No	imp_ana_ra_thresh2	Pacing threshold [V]	scale	n.a.
implantation_analyzer_data	No	imp_ana_ra_pulse	at Pulse width [ms]	scale	n.a.
data_SAR	Yes	imp_ana_ra_thresh_0 ⁵ ₂₅	Pacing threshold [V] at Pulse width 0.5 ms	scale	n.a.

A pacing threshold must always consist of amplitude and duration (pulse width). It is not reasonable to report one without the other.

Here, the CIP requires using 0.4 ms, but it can be expected that other pulse durations were used because different analyzer devices which are being used in the investigational centers have different standard settings.

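### SAP footnote 6 does not itself enforce the rule that upgrade and exchange patients belong to group A only: one recorded as group AB enters the Plexa confirmatory analysis

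*SAP*

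**What the plan says.** **Protocol.** Inclusion criterion 2 (8.8.2) is one item with a group-specific meaning: de novo "implantation or upgrade/exchange^h (group A only) from existing" systems. Footnote h gives the reason: "Upgrade or exchange is not available for patients in group B due to possible interference between the previous implanted RV lead" and the new Plexa lead, so that the source of an adverse event might not be separable. Section 8.8.2 also states that "All of the following inclusion criteria have to be fulfilled for enrollment of the patient to the clinical trial". In Table 7 (9.1) the criteria are verified at enrollment, while the row "Decision on group participation" is marked at implantation.

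Section 9.3 makes two statements. Its first paragraph says: "If both devices are implanted patients will participate in both groups as long as enrollment in both groups is still ongoing". Its next paragraph says that planned upgrades or exchanges "can also be included in the study (group A only").

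**SAP.** Section 7.3 says "the Plexa analysis set consists of all patients in group B and in group AB, who met all in- and exclusion criteria". Footnote 6 implements this as consent, TIINCL01 to TIINCL06 all Yes, TIEXCL01 to TIEXCL07 all No, imp_group equal to B or AB, and neither of two early-termination reasons. For the primary endpoint, footnote 99 (23.2) adds only a timing condition. The type of implantation is held in imp_category, whose first value is "De novo CRT-D / ICD implantation"; the other values are upgrade from pacemaker, upgrade from ICD, and exchange. The SAP lists this variable in 10.2 (Ilivia) and not in 19.2 (Plexa).

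**The concern.** The criterion differs by group, but the code represents it by one Yes/No flag common to both analysis sets. A patient upgraded from a pacemaker is eligible for group A, so TIINCL02 is correctly Yes. If that patient receives an Ilivia device and a new Plexa lead, the combination recommended in Protocol 8.1, a site following the first paragraph of 9.3 would record AB. Footnote 6 then admits the patient.

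The Plexa primary endpoint counts serious device effects possibly or securely related to the lead. Relatedness is the judgement that footnote h considers at risk when an earlier lead is present. The same analysis set feeds the Kaplan-Meier estimate (SAP 23.7) and the sensing and pacing endpoints (SAP 24 and 25). Because 19.2 does not report imp_category, the Plexa chapters would not show that such patients are there.

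**Working it through.** **1. The code applied to an upgrade or exchange patient.** All other conditions are taken as met. Footnote 5 defines the Ilivia set, footnote 6 the Plexa set.

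| TIINCL02 | imp_group | Ilivia set | Plexa set |
|---|---|---|---|
| Yes | A | in | out |
| Yes | B | out | in |
| Yes | AB | in | in |
| No | A, B or AB | out | out |

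The Protocol requires such a patient to be in the Ilivia set and out of the Plexa set. With imp_group = AB, no value of TIINCL02 gives that result: Yes admits to both sets and No removes from both. Only imp_group = A works.

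**2. The plan's own sample size.** Inputs: null SADE-free rate 90% (Protocol 8.3.1.2), assumed rate 97% (11.2), one-sided level 1.25% and power at least 90% (11.3), drop-out 10% (11.4). Let X be the number of event patients among n. The test passes with at most c event patients, where c is the largest k with P(X ≤ k | n, 0.10) ≤ 0.0125. Power is P(X ≤ c | n, 0.03).

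- n = 166: P(X ≤ 8) = 0.01215 and P(X ≤ 9) = 0.0260, so c = 8 and power is 93.6%.
- 166 is the smallest n from which power stays at or above 90%, and 166 / 0.9 = 184.4, rounded up to 185.

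Both stated figures, 166 and 185, reproduce.

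**3. One patient at the boundary.**

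- n = 165: P(X ≤ 8) = 0.0129, above 0.0125, so c = 7.
- Suppose 165 eligible patients with 8 event patients: the test fails. Adding one ineligible event-free patient gives 8 of 166, which passes.
- Suppose 166 eligible patients with 8 event patients: the test passes. Adding one ineligible patient with an event gives 9 of 167. The limit is 8 at n = 166 and at n = 168, hence also at 167, so the test fails.

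The error can act in either direction.

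**4. What removal would cost.** The documents give no share of upgrade or exchange patients among AB patients, so the shares below are assumptions.

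| Share removed from 166 | n left | Limit c | Power at 97% |
|---|---|---|---|
| 0% | 166 | 8 | 93.6% |
| 5% | 158 | 7 | 89.6% |
| 10% | 149 | 6 | 83.8% |
| 20% | 133 | 5 | 78.9% |

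If 10% were removed from 185 with no other loss, 166 would remain and power would be 93.6%.

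**The case against.** The strongest reply is that the rule does reach the SAP, through imp_group. The restriction to group A stands in the synopsis, criterion 2, footnote h and 9.3. Protocol 8.1 says that patients with both devices can, not must, belong to both groups, and that participation has to comply with the protocol for the group concerned. In 9.3 the specific sentence on upgrades can be read as governing the general one. A site that reads it so records A, and footnote 6 then works. A wrong AB entry would be a deviation, open to monitoring and data queries. The eCRF wording of TIINCL02 is abbreviated in the SAP, and any edit check between imp_category and imp_group is not shown.

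This stands as a limit on the point. A reader might infer that the SAP ignores the rule altogether, or that ineligible patients are certain to be in the Plexa set; the documents support neither. It does not close the gap: the visible safeguard is one site entry, made under two sentences that disagree, and the analysis code has no second check behind it.

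Two further replies are fair. The drop in the limit from 8 to 7 follows the loss of any patient for any reason, so it is not peculiar to this gap. Footnote h speaks of possible interference, and an adjudication board re-examines relatedness, with two evaluations that must agree and divergences reported (SAP 23.2). A reader might infer that events in these patients can never be attributed, or that the primary result is biased; the text does not go that far.

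**Conclusion.** The gap is real and confined to the code. An upgrade or exchange patient recorded as AB is admitted to the Plexa analyses against criterion 2 and footnote h, and footnote 6 cannot prevent it. It takes effect only if a site makes that entry and, for the primary analysis, if the timing condition in footnote 99 is also met. Whether any such patient exists cannot be known from the documents.

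A reader might take this to mean that the group B sample size or power is wrong. It is not: 166 and 185 reproduce under the stated assumptions. What can be said about size is that one such patient could change the decision if the result falls at the pass limit, and that away from the limit a few would have little effect on the test. A correction before analysis is justified because the set is confirmatory and the change is small.

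**What to change.** 1. In SAP footnote 6, add the condition that imp_category is not upgrade from pacemaker, upgrade from ICD, or exchange of ICD / CRT-D. Word it as an exclusion of these values and not as a requirement for de novo: the SAP lists imp_category only for Ilivia, so its completeness in B-only patients is not shown, and a missing value must not remove an eligible patient. Query missing values.
2. Report imp_category in SAP 19.2.
3. Leave footnote 5 unchanged, so that these patients stay in the Ilivia set.
4. List any upgrade or exchange patient recorded as AB, with SADEs, outside the Plexa confirmatory set.
5. Reconcile the two sentences in Protocol 9.3 with criterion 2 and footnote h.

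The cost is one condition on a variable already collected, one table row, one listing and a wording change. The downside is that the Plexa set may lose a few patients, with the effect on the limit and power shown above. If there are no such patients, no result changes.

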The safety of the Plexa right ventricular lead will be evaluated by asking the investigator to record any adverse event. While all adverse events have to be recorded throughout the study, only the Serious Adverse Device Effects (SADE) possibly or securely related to the Plexa ICD lead (SADE-d_{Plexa}) until 3-month follow-up and meeting predefined criteria (see 18.11) are counted for this primary endpoint. Securely procedure related Serious Adverse Device Effects (SADE-p_{Plexa}) are not counted. The primary hypothesis evaluates the SADE-d_{Plexa} free rate (Plexa_{SADE_free}). It is expected, that the rate will be significantly above 90%, the corresponding hypotheses definitions are:

Null hypothesis: $H_{0_Plexa} : Plexa_{SADE_free} \leq 90\%$

Alternative hypothesis: $H_{A_Plexa} : Plexa_{SADE_free} > 90\%$

The parameter of interest "Plexa_{SADE_free}" is the SADE-free rate per patient, which will be calculated by

$$Plexa_{SADE_free} = [1 - \text{number of patients with one or more Plexa-related SADEs (SADE-d}_{Plexa}\text{) until 3-month follow-up divided by all patients in the analysis set}] * 100\%.$$

SADEs will be adjudicated by an internal adjudication board, whereby the seriousness and device relatedness will be re-examined. If any amply documented external physical influence (e.g. accident, sport, twiddling) or medical AE caused the SADE, it does not contribute to this endpoint. SADEs that occur later than the 3-months follow-up do not contribute to this endpoint.

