8.8.4 Drop-out criteria

8.8.4.1 Mandatory drop-out according to protocol

The investigator shall exclude a patient due to the following reasons (defined as drop-out according to protocol):

- **Group A:** Patient is not implanted with a member of the Ilivia ICD family for any reason
- **Group A:** Patient in whom explantation or replacement of the Ilivia ICD is performed
- **Group B:** Patient in whom implantation of Plexa ICD lead was planned but not performed
- **Group B:** Patient in whom explantation, replacement or repositioning of the Plexa ICD lead is performed
- Patient undergoes heart transplantation or receives ventricular assist device during the course of the study.

If a patient participates in both groups, drop-out in one group does not result in drop-out of the other group, thus the patient can continue participation in the other study group.

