8.8.5 Point of enrollment and study termination

The point of enrollment is defined as the date of signature of the informed consent form by the patient. Study related procedures, documentation and collection/following of adverse events will start from this day on.

The point of study termination is defined as date of 6-month follow-up for patients with regular study termination.

For a non-regular study termination, the following rules apply:

- If none of the investigational devices could successfully be implanted, date of study termination should be the date of the last unsuccessful implantation attempt.
- In case of replacement or repositioning of the Plexa ICD lead in patients of **Group B** date of study termination should be date of revision.
- In case of withdrawal of a patient's consent, date of study termination should be the date of withdrawal of consent.
- In case of patient death, the date of study termination should be the date of the patient's death.
- If patient is lost to follow-up, date of termination should be the date of last contact of the physician to the patient.
- If patient is defined as drop-out patient for any other reason, date of study termination should be the date of latest medical information of the patient (e.g. follow-up, IEGM).

Study related procedures and documentation should end at the day of study termination. However, Serious Adverse Device Effects which are not resolved at date of study termination will be followed for up to 4 weeks after study termination of the respective patient.

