11 STATISTICAL CONSIDERATIONS

11.1 Statistical design, method and analytical procedures

The BIO|MASTER.Ilivia Family / Plexa study is a prospective, single-arm, non-randomized, open clinical study.

For both primary hypotheses exact binomial tests are carried out. All endpoints are analyzed per-protocol (PP), whereby the analysis sets are defined for each hypothesis separately. Patients without written informed consent are not included in any analysis set. More details as already presented in section 8.3 will be presented in the Statistical Analysis Plan, which will be completed after finalizing this CIP.

For continuous variables descriptive statistics (mean, standard deviation, minimum, 1. quartile, median, 3. quartile and maximum) will be calculated. For nominal variables absolute numbers and relative frequencies based on the non-missing data will be determined. Ordinal data are described by the 1. quartile, median, and 3. quartile as well as the absolute numbers and relative frequencies based on the non-missing data of each category.

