11.3 Level of significance and the power of the study

The 2-sided level of significance is $\alpha = 2.5\%$ for each alternative hypothesis (1-sided 1.25% significance level). Thus, the 2-sided significance level of the global hypothesis of 5% (1-sided 2.5% significance level) is maintained.

A minimum statistical power for primary hypothesis 1 of 80% and a minimum power of 90% for primary hypothesis 2 were used for sample size calculation.

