7.2. Ilivia Analysis Set

The analysis set Ilivia consists of all patients in group A and in group AB, who met all in- and exclusion criteria. Patients who did not come in contact with any Ilivia device are not included in the analysis set.

Data file, identifier patient_display_id_full	Variable name	Variable label	Variable level	Nominal values
enrollment	DMSUBIC	Patient has provided written informed consent	nominal	Yes /No
enrollment	TIINCL01 TIINCL02 TIINCL03 TIINCL04 TIINCL05 TIINCL06	Inclusion criteria [...]	nominal	Yes /No
enrollment	TIEXCL01 TIEXCL02 TIEXCL03 TIEXCL04 TIEXCL05 TIEXCL06 TIEXCL07	Exclusion criteria [...]	nominal	Yes /No
implantation_general_data	imp_group	Patient Group		Device of the Ilivia family (group A) Plexa right ventricular lead (group B) Both Ilivia and Plexa (group AB)
study_termination	end_early_a	Reason for early study termination	nominal	Implantation of Ilivia ICD family was planned but not performed (patient did not come in contact with the investigational device) [...]
study_termination	end_early_ab	Reason for early study termination	nominal	Implantation of Ilivia ICD family and Plexa lead were planned but not performed (patient did not come in contact with the investigational devices) [...]
data_SAR	analysis_set_Ilivia_SAR ⁵	Analysis set Ilivia	nominal	Yes / No

A list of all patients with early drop-out with patient ID, patient group and reason for early study termination will be provided.

⁵ IF DMSUBIC = Yes AND
TIINCL01 = Yes AND TIINCL02 = Yes AND TIINCL03 = Yes AND
TIINCL04 = Yes AND TIINCL05 = Yes AND TIINCL06 = Yes AND
TIEXCL01 = No AND TIEXCL02 = No AND TIEXCL03 = No AND
TIEXCL04 = No AND TIEXCL05 = No AND TIEXCL06 = No AND TIEXCL07 = No AND
(imp_group = ... (group A) OR imp_group = ... (group AB)) AND
end_early_a ≠ Implantation of Ilivia ICD family was planned but not performed ... AND
end_early_ab ≠ Implantation of Ilivia ICD family and Plexa lead were planned but not performed ...
THEN analysis_set_Ilivia_SAR = Yes
ELSE analysis_set_Ilivia_SAR = No

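### SAP footnotes 5 and 6 do not fully code the no-contact exclusion for patients recorded in both groups, so a patient who had contact with only one device can remain in the other device's analysis set

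*SAP*

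**What the plan says.** The prose rule is clear for both devices. SAP 7.3 states: "Patients who did not come in contact with any Plexa lead are not included in the analysis set". SAP 7.2 states: "Patients who did not come in contact with any Ilivia device are not included in the analysis set".

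Footnotes 5 (Ilivia) and 6 (Plexa) turn this into code. Footnote 6 requires consent, all eligibility criteria, imp_group equal to B or AB, an end_early_b value other than the Plexa not-performed reason, and "end_early_ab ≠ Implantation of Ilivia ICD family and Plexa lead were planned but not performed". Footnote 5 mirrors this with end_early_a. Neither footnote tests the implanted device or lead model, although the SAP lists imp_dev (10.2) and imp_rv_model (10.2 and 19.2).

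The protocol foresees that a patient may leave one group only. Under 8.8.4.1, "drop-out in one group does not result in drop-out of the other group". For termination dates, 8.8.5 provides: "If none of the investigational devices could successfully be implanted, date of study termination should be the date of the last unsuccessful implantation attempt". It has no explicit rule for one of two devices not being implanted. Its residual rule for other drop-outs is the date of the latest medical information.

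**The concern.** A patient planned for both devices may receive an Ilivia ICD with a different RV lead, or a Plexa lead with a different ICD. If that patient is recorded as AB, the coded AB condition does not apply, because one of the two implantations did take place. The patient can then stay in the set of a device never encountered.

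Two kinds of result could be affected. In the Plexa RV sensing and pacing endpoints, both tested against 93%, another lead's performance could be credited to Plexa. In the primary SADE-free rates, a patient who never had contact with the device cannot have its SADE, so any such patient adds a certain success to the denominator.

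**Working it through.** **Path of an AB patient with no Plexa contact (implantation = day 0).** The Ilivia side mirrors this.

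| Record | Plexa analysis set (fn 6) | Primary endpoint set (fn 3 and 99) |
|---|---|---|
| Neither device performed | removed | removed |
| end_early_b holds the Plexa not-performed reason | removed | removed |
| end_early_b empty, group B termination dated day 0 | stays | removed by the 60-day rule |
| end_early_b empty, group B termination dated day 61 or later | stays | stays, event-free |
| end_early_b empty, group B termination not recorded (overall end about day 180) | stays | stays, event-free |

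The last two rows arise because footnote 3 takes the group-specific date only if group B termination is recorded and otherwise takes the overall end date. Footnote 99 then admits any end date at least 61 days after implantation.

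**Secondary endpoints.** SAP 24.1 and 25.1 use the Plexa analysis set with non-missing 3-month RV data and have no 60-day rule. All of the last three rows can therefore reach these endpoints. CIP 8.5.11 has group A patients assessed for sensing and pacing in every available channel at 3 months, and CIP 8.7.2 leaves the group A RV lead to free choice. The data for a non-Plexa lead would thus exist in the same variables (fu3_perf_rv_sens, fu3_perf_rv_pac).

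**Primary endpoints: inputs.** The test is exact binomial (CIP 11.1: "For both primary hypotheses exact binomial tests are carried out"). The level is 1.25% one-sided (CIP 11.3). The null SADE-free rate is 90%, so the null event rate is 10% (CIP 8.3.1). The planned sizes are 94 and 166 analysed, 105 and 185 enrolled, with assumed rates of 98% and 97% (CIP 11.2).

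**The plan's own figures.** The event limit c is the largest value with P(X ≤ c | n, 0.10) ≤ 0.0125.
- Group A: n = 94 gives c = 3, error 1.246%, power 88.0% at 98%. This is the smallest n with at least 80% power.
- Group B: n = 166 gives c = 8, error 1.215%, power 93.6% at 97%. Power first reaches 90% at n = 152, but stays there for all larger n only from 166.
- Enrolment: 94/0.9 = 104.4, so 105; 166/0.9 = 184.4, so 185.

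The stated sizes reproduce. Both lie on a step of the event limit: n = 93 allows 2 events and 94 allows 3; n = 165 allows 7 and 166 allows 8.

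**Effect of k unexposed patients inside the analysed total.** The limit is set by the total, but only n − k patients can have an event, so the error is P(X ≤ c | n − k, 0.10). The documents give no k; these values are assumptions.

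| k | Group A: P(X ≤ 3 given 94 − k) | Group B: P(X ≤ 8 given 166 − k) |
|---|---|---|
| 0 | 1.25% | 1.22% |
| 1 | 1.34% | 1.29% |
| 5 | 1.82% | 1.64% |
| 10 | 2.64% | 2.19% |

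**When nothing changes.** The limit is 3 for every n from 94 to 109, which covers all 105 planned group A patients, and 8 for every n from 166 to 179. If at least 94 (or 166) exposed patients are analysed, unexposed ones added up to a total of 105 (or 179) leave the test decision as it was. The estimated rate would still rise slightly.

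**The case against.** The strongest reply is that the gap may be closed by forms that the documents do not show. Footnote 6 tests end_early_b for every patient in B or AB, not only for group B. If that field is filled when an AB patient leaves group B, the patient is already out. The remaining end_early_ab values are abbreviated in the SAP and may include one-device reasons, although the code as written would not use them.

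The affected group may also be very small. CIP Table 7 places the group decision at implantation, and CIP 9.3 ties membership of both groups to both devices being implanted. A patient given Ilivia with another RV lead should then be recorded as group A, which footnote 6 removes. The not-performed reason under AB shows that AB can be recorded as planned when neither device goes in; it does not show this for one of two.

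CIP 8.1 also says that, once a patient leaves one group, only data for the still active group are used. Finally, a mismatch would be visible: lead and device models are tabulated for the analysis sets, and early drop-outs are listed with group and reason.

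All of this stands, and it limits frequency and consequence. It does not make the code match the prose. No SAP footnote implements the CIP 8.1 restriction, and a tabulated mismatch does not itself remove anyone from an analysis.

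A reader might infer that the primary rates are biased upward as planned, or that the sponsor means to count other leads as Plexa. The documents support neither. Remaining in the analysis set does not by itself make a patient a primary success, because of the 60-day rule, and both the SAP prose and CIP 8.1 state the opposite intent.

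**Conclusion.** The coded sets are narrower in their exclusions than the SAP's own rule. This holds unless end_early_a and end_early_b are also filled for AB patients, on which the SAP is silent.

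The clearer exposure is in the Plexa RV sensing and pacing endpoints, where no later SAP filter applies and a non-Plexa lead could be counted against CIP 8.1. For the primary endpoints the effect is conditional: the patient counts as an event-free success only if group termination is unrecorded or dated day 61 or later. CIP 8.8.5 does not rule that out.

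The size is unknown and probably small. The error figures above hold only when the analysed total reaches 94 or 166 with unexposed patients included while the exposed number falls short of it; they illustrate sensitivity and do not predict a result. Where the gap does act on the primary endpoints, it favours the device. The correction is worth making because these are confirmatory analysis sets and the change is simple.

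**What to change.** - **Footnote 6:** for imp_group = AB, also require a Plexa model in imp_rv_model, or a documented contact or implantation attempt with a Plexa lead.
- **Footnote 5:** for imp_group = AB, also require an Ilivia-family device in imp_dev, or a documented contact or attempt with one. Keeping attempts in both footnotes preserves the contact rule in the prose.
- **Group end date (footnotes 2 and 3):** for a device that was never implanted, set the group-specific termination date to the implantation (attempt) date.
- **While editing footnotes 72 and 99:** bracket the two date conditions joined by OR, so that the analysis-set flag governs both, as the SAP's subset wording intends.

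The model variables are already collected. The SAP does not name a variable for an attempt, so its source must be stated. The analysed number may fall by a few patients, which matters because 94 and 166 sit on steps of the event limit.
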